### 3. INTRODUCTION AND OVERVIEW

This statistical analysis plan (SAP) is intended to provide a detailed description of the statistical methods and procedures that will be used to evaluate and report the results of the study outlined in protocol CPI-IFE-007 (Amendment 04a, dated March 10, 2025). This SAP incorporates analyses for both the double-blind treatment period and open-label extension periods as described in the protocol, including the use of natural history study data as a historical comparator and supplemental placebo group.

Data will be analyzed by Symbiance Pvt. Ltd. using Statistical Analysis Software (SAS®, version 9.4).

A separate document contains the table, figure, and listing (TFL) specifications.

#### 3.1 Study Design

This is a double-blind (DB), placebo-controlled, multicenter, dose-ranging study with an open-label extension (OL) to determine the safety, pharmacokinetics, and efficacy of two dose ranges of oral ifetroban in subjects with DMD.

[figure not shown]
Subjects who meet eligibility criteria will be randomly assigned to one of three treatment groups 1:1:1 ratio, low-dose ifetroban, high-dose ifetroban or placebo, and dosed based on weight. Each treatment group will be evaluated by eight subjects with early stage (LVEF >45%) and eight subjects with advance stage (LVEF 35% - 45%) DMD for at least six months and a maximum of 12 months. Subjects who complete 12 months of treatment will be eligible to participate in an OL extension ([Figure 1](#)).

All subjects who receive IMP will be assessed for safety. All subjects with at least one efficacy assessment post-baseline will be evaluated for efficacy. Blood and urine will be collected for standard and novel cardiac biomarkers.

The clinical study will be conducted with two periods:

- Screening period of up to 12 weeks.
- Randomized ifetroban/placebo treatment period of 12 months.
- Subjects who complete 12 months of treatment will be eligible to participate in an OL extension.

**Figure 1 Study Design**

CBC = complete blood count; CMP = comprehensive metabolic panel; Coags = coagulation factors; ECG=electrocardiogram, Echo= echocardiography; QMT= quantitative muscle testing; PFT= pulmonary function test; QoL = quality of life; LVEF = left ventricle ejection fraction; CMR=cardiac MRI; PE = physical exam with vitals; PK=pharmacokinetics; W= week, M=month

### 3.2 Study Objectives

#### 3.2.1 Primary Objectives

The primary objective of the trial is to assess the safety of oral ifetroban in male subjects with Duchenne Muscular Dystrophy (DMD).

#### 3.2.2 Secondary Objectives

To evaluate the pharmacokinetics and efficacy of oral ifetroban.

#### 3.2.3 Exploratory Objectives

- Evaluate novel biomarkers for diagnosis and monitoring of cardiomyopathy in DMD.
- Evaluate changes in daily life activity and quality of life.

### 3.3 Study Endpoints

Definitions for study endpoints, including baseline values, are specified in [Section 4.4.1](#). Unless otherwise noted, all data, including baseline up to, and including week 52 will be analyzed.

Subjects who discontinue the study treatment before week 52 will have their data imputed last observation carried forward (LOCF).

[Section 4.2](#) describes how to handle missing data points.

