8 STUDY VISITS AND PROCEDURES

8.1 Overview – Schedule of Time and Events

This clinical study will consist of a 12-week Screening Period (Week -12 to Week 0) and a 12-month Treatment Period (Month 0 to Month 12). The study visits occur on the planned dates relative to the first dose of IMP as scheduled. The visit schedule should be adhered to within the visit window indicated.

If a subject is prematurely discontinued from treatment, all assessments planned at the End of Treatment visit should be performed. Prior to all screening assessments, after discussion of participation in the study, the written consent form must be signed and dated. Although the screening assessments for this study are grouped under the heading of a single visit in this protocol, it is possible for them to be performed over more than one site visit if necessary, as long as the twelve-week screening period relative to the first dose of IMP is respected. Furthermore, the site may split the on-site study visits during the treatment period (Day 0, Month 6, Month 12 & Month 24, if applicable) into two visits no more than 7 calendar days apart provided that each of the visit days remain within the protocol established window for the on-site study visits. Subjects that fail screening for exclusion criteria, for example concomitant medications, acute illness (upper respiratory tract infection), required drug-specific discontinuation periods or laboratory tests, may be rescreened for study eligibility.

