After six months of treatment, subjects will return to the site for Month 6 Treatment Visit.

- Record all medication use with start date and dose; check for prohibited medications.
- Inquire about AEs/Serious Adverse Events (SAEs) and IMP tolerability.
- Confirm compliance (subject diary & pill counting) & dietary requirement.
- Perform ECG, a physical exam with vital signs (blood pressure, heart rate, respiration rate, body temperature, weight).
- Obtain blood samples for clinical laboratory tests:
 - Complete Blood Count with differential: must include hemoglobin, hematocrit, platelet count, total white blood cell count with five-part differential count, and total red blood cell count.

- Comprehensive Metabolic Panel: must include serum creatinine, blood urea nitrogen, glucose, total protein, albumin, total bilirubin, alanine aminotransferase, aspartate aminotransferase, alkaline phosphatase, electrolytes (sodium, potassium, chloride), calcium, bicarbonate, and creatine phosphokinase.
- Coagulation Factors: prothrombin time reported as the international normalized ratio (INR) value (PT-INR), partial thromboplastin time (PTT or aPTT).
- Collect urine and blood samples for eicosanoid metabolites and other biomarkers.
- Dispense and administer IMP.
- Optional Month 6 CMR (\pm 7 day window). If Month 6 CMR is declined, a mandatory ECHO should be performed.
- Month 6 PFT including PEF, FVC, FEV1, MIP, and MEP
- Month 6 PedsQL, GI module & NMM
- Month 6 QMT & Actigraphy
- Schedule appointment for next visit.

Should the subject report a new or worsening symptom, additional safety phone calls and/or safety visits may be scheduled at the investigator's discretion and safety labs performed. Any new or worsening abnormal lab should be followed and repeated until back to baseline or resolved.

Month 9 At-home Quality-of-Life surveys

- Complete and return Month 9 at-home PedsQL, GI module & NMM.

Month 12 End of Treatment Visit

After six additional months of treatment, subjects will return to the site for Month 12 End of Treatment Visit.

- Record all medication use with start date and dose; check for prohibited medications.
- Inquire about AEs/Serious Adverse Events (SAEs) and IMP tolerability.
- Confirm compliance (subject diary & pill counting) & dietary requirement.

- Perform ECG, a physical exam with vital signs (blood pressure, heart rate, respiration rate, body temperature, weight).
- Obtain blood samples for clinical laboratory tests:

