11.7 Methods for Handling Missing Data

All missing data will be queried. Missing data which are not retrievable through queries will not be imputed. The only exception to this is one supportive analysis with missing LVEF at Month 12 imputed by LVEF at Month 6; subjects missing LVEF at both Month 6 and Month 12 will be excluded from this supportive analysis.

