### **3.6 Analysis Sets**

### **3.6.1 Intention-To-Treat (ITT) Population**

The Intent-To-Treat (ITT) Population will consist of all treated subjects with at least one post-baseline assessment.

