## 4.2 Missing Data

For the primary endpoint and key secondary efficacy endpoints, missing data will not be imputed in the primary analyses. A supportive sensitivity analysis for the Month 12 LVEF endpoint will be conducted where missing LVEF values at Month 12 will be imputed using Month 6 values, if available. Subjects missing LVEF at both Month 6 and Month 12 will be excluded from this supportive analysis. For long-term analyses in the open-label extension, subjects missing data at key timepoints (Month 24, Month 36) will be excluded from the respective analyses. No other imputation will be provided for any endpoint.

Since LVEF is a key efficacy endpoint, the pattern of missing data will be carefully evaluated to assess potential bias. The frequency and reasons for missing LVEF measurements will be

summarized by treatment group to determine whether missingness might be related to treatment or disease progression. If systematic differences in missing data patterns are identified between treatment groups, additional sensitivity analyses may be conducted using multiple imputation methods that account for the potential relationship between the likelihood of missing data and the unobserved outcomes. This would involve creating multiple complete datasets based on observed covariates and outcomes, analyzing each dataset, and combining results according to Rubin's rules. These additional analyses would be considered exploratory and would be used to evaluate the robustness of the primary analysis approach.

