#### **4.4.4 Multiple Comparisons/Multiplicity**

Multiplicity and multiple comparisons do not apply to these secondary and exploratory objectives. No adjustments will be made for multiple comparisons or multiplicity. Changes to Protocol Specified Analysis

There are no changes to the protocol specified analyses.

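### SAP 3.3 carries values forward for treatment discontinuers whom SAP 4.2 and protocol 11.7 leave missing; the SAP's pulmonary-effort, baseline and Month 36 rules also need correction

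*SAP*

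**What the plan says.** **Missing data.**
- SAP 3.3: "Subjects who discontinue the study treatment before week 52 will have their data imputed last observation carried forward (LOCF". The next line refers to 4.2 for missing data points.
- SAP 4.2 rules out imputation in the primary analyses of the primary and key secondary endpoints. It allows one supportive analysis that replaces a missing Month 12 LVEF with the Month 6 value, then closes: "No other imputation will be provided for any endpoint". Its next paragraph adds that, if missingness differs by arm, "additional sensitivity analyses may be conducted using multiple imputation methods".
- Protocol 11.7: "Missing data which are not retrievable through queries will not be imputed". Its sole exception is the same supportive LVEF analysis.
- SAP 4.4.4: "There are no changes to the protocol specified analyses". SAP section 8, on changes from the protocol, is marked not applicable.

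**Pulmonary function.** SAP 6.2.3 takes the maximum of three efforts. SAP 9.1.1 takes the highest only if it is within 10% of the middle one, and the middle one otherwise.

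**Baseline.** SAP 4.4.1 uses one definition for both periods: the last available value up to the start of ifetroban. SAP 14.3.4 uses pre-treatment values for the double-blind period and Month 12 for the open-label period.

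**Three-year analysis.** SAP 6.4.1 summarises change from baseline and from Month 36. Protocol 6.5 and 11.8.6 use Month 12 as the second reference.

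**The concern.** These rules produce different analysis datasets, and the SAP text does not say which one governs.

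The LOCF conflict matters most because it reaches a tested result. Change in LVEF and strain is compared between arms by Wilcoxon test (protocol 11.8.3, SAP 6.2.1), and the design has 8 subjects per arm within each disease stage. In groups of that size, it can matter whether a few discontinuers enter with carried values or are absent.

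The sentence also sits above the whole endpoint list. As worded it reaches PFT, PedsQL, and the laboratory, ECG and vital-sign changes in SAP 3.3.1. If the choice is left open, it could be made after treatment codes are known.

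**Working it through.** **1. How many subjects might be involved.**
- SAP 3.4 assumes 10% dropout and recruits 54 for 48. Check: 48 / (1 − 0.10) = 53.3, rounded up to 54, which reproduces. Implied losses: 54 − 48 = 6, or 0.10 × 54 = 5.4.
- Protocol 11.1 assumes 25% and recruits 60 for 48. 60 is 48 × 1.25, whereas 48 / (1 − 0.25) = 64. Implied losses: 60 − 48 = 12, or 0.25 × 60 = 15.
- If all were treatment discontinuers without a Month 12 value, spread evenly over three arms, the share per arm runs from 2 of 18 (11%) to 5 of 20 (25%). An uneven split would exceed this in some arm, so it is not a ceiling.

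**2. LOCF against SAP 4.2.** Illustrative subject: baseline LVEF 50, treatment stopped early, no Month 12 scan.

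| Month 6 CMR | SAP 3.3 | SAP 4.2, main | SAP 4.2, supportive |
|---|---|---|---|
| 47 | 47 − 50 = −3 | missing | −3 |
| not done | 50 − 50 = 0 if baseline may be carried (3.3 does not say) | missing | excluded |

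The second row can occur. The Month 6 CMR is optional: "If Month 6 CMR is declined, a mandatory ECHO should be performed". SAP 3.6.1 admits to ITT "all treated subjects with at least one post-baseline assessment", without requiring that assessment to be a CMR. For strain, PFT and PedsQL, 4.2 has no supportive analysis, so a carried value has no place there.

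**3. Pulmonary effort.** Let H and M be the highest and middle efforts. SAP 9.1.1 selects M when (H − M)/H > 0.10, that is, when M < 0.90 H. Whenever the two rules disagree, they differ by more than 10% of H. Illustrative values (L):
- Baseline 1.75 / 1.80 / 2.10: (2.10 − 1.80)/2.10 = 14.3%, so 6.2.3 gives 2.10 and 9.1.1 gives 1.80.
- Month 12 1.80 / 1.90 / 1.95: (1.95 − 1.90)/1.95 = 2.6%, so both give 1.95.
- Change: 1.95 − 2.10 = −0.15 under 6.2.3; 1.95 − 1.80 = +0.15 under 9.1.1.

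For MIP, 6.2.3 words the absolute value as taken after the maximum. If MIP were recorded as negative, −60 / −50 / −40 would give |−40| = 40, the weakest effort, against 60 if absolute values came first. The documents do not state the sign convention.

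**4. Baseline, read literally.**
- A placebo subject who enters the extension starts ifetroban at Month 12. The Month 12 value then becomes the baseline, and the double-blind change at Month 12 is zero whatever happened during the year.
- A placebo subject who never takes ifetroban has no baseline.
- A subject randomised to ifetroban has an open-label baseline that predates the double-blind period, against Month 12 in 14.3.4.

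**5. Month 36.** The value at Month 36 minus the value at Month 36 is zero for every subject. The protocol's change from Month 12 at Month 36 is then not summarised.

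**The case against.** The strongest reply is that the plan's position on missing data is clear. Protocol 11.7, protocol 11.8.3 and SAP 4.2 agree, one stray sentence departs from them, and the line after it points to 4.2. That shows what was probably intended. It does not remove the conflict, because 3.3 is worded as a rule and the text it points to forbids it. Nor can 3.3 be read as covering discontinuers while 4.2 covers other gaps: neither 4.2 nor protocol 11.7 makes that exception.

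Second, few subjects may be affected. Protocol 8.1 says: "If a subject is prematurely discontinued from treatment, all assessments planned at the End of Treatment visit should be performed". If that is done, fewer will lack late data, so this lowers the likely size.

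Third, SAP section 10 places derivation rules in separate documents, which are not available here and may already settle some points. They cannot make the SAP agree with itself or with the protocol.

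Fourth, PFT is descriptive in the randomised comparison. That stands. SAP 4.5.3, however, applies the Wilcoxon test to key secondary endpoints in the supplementary natural history comparisons, and 3.3.2 lists PFT among them. For the double-blind comparison, 14.3.7 names only LVEF and strain, and protocol 11.8.3 only CMR parameters.

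Fifth, the intended baseline can be inferred. SAP 4.4.1 itself goes on to refer to the study drug, and 14.3.2 and 14.3.4 use pre-dose values, although those two sections concern natural history matching. This makes the repair easy; the rule as written is still wrong.

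**Conclusion.** The SAP should be corrected before lock. Two contradictions, LOCF and the pulmonary effort rule, are plain in the text. The baseline rule is a substantive error as worded, with a recoverable intention. The Month 36 reference is an evident slip that loses a protocol analysis.

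The number of subjects affected by LOCF is unknown. The range of about 5–6 (SAP) to 12–15 (protocol) rests on planning assumptions and bounds no arm. How often the two pulmonary rules disagree cannot be known from the documents.

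A reader might infer more than this supports:
- *That LOCF favours ifetroban or placebo.* The documents give no pattern of discontinuation by arm, so no direction follows.
- *That the primary result is compromised.* The TEAE percentage is not affected. LOCF would reach only the laboratory, ECG and vital-sign changes that SAP 3.3.1 lists with it.
- *That placebo changes will actually be computed from Month 12.* The other passages point to a pre-dose baseline.
- *That MIP selection is wrong.* This depends on an unstated sign convention and is a query only.

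**What to change.** Before database lock and unblinding:

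1. **Missing data.** Delete the LOCF sentence in SAP 3.3. In 4.2, state that no missing visit-level value will be imputed except in the supportive Month 12 LVEF analysis and, if triggered, the exploratory multiple imputation. Add that the PedsQL item-level scoring rules (9.1.3–9.1.5), partial-date rules (14.2) and AE-relationship rule (7.1) are unaffected; a blanket ban would contradict them, as the present closing sentence already does. List the multiple imputation in section 8 as an addition to protocol 11.7, and amend the no-changes sentence in 4.4.4 to match.
2. **Pulmonary function.** Choose one best-effort rule before unblinding and state it once, for example in 9.1.1 with 6.2.3 referring to it. Apply it equally at all visits and, where effort-level data exist, to natural history subjects. Confirm the MIP sign convention; if values are negative, take absolute values before selecting the effort.
3. **Baseline.** In 4.4.1, define double-blind baseline as the last non-missing value on or before the first dose of double-blind drug, whether ifetroban or placebo. Use Month 12 for change during the extension and for open-label matching. Use double-blind baseline for the analyses from baseline to Month 24 and to Month 36.
4. **Three-year analysis.** In 6.4.1, replace Month 36 with Month 12 as the reference.

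The cost is SAP wording and, where needed, the derivation specification. No new data, sample size change or change in trial conduct is required.

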### 3.3.1 Primary Endpoints

Safety Endpoints:

Safety assessment will be based on treatment emergent adverse events (TEAEs), laboratory abnormalities, ECG, vital signs, and physical examination.

- Percentage of subjects with one or more TEAE
- Change from baseline in laboratory variables and incidence of markedly abnormal laboratory values and shifts from baseline of laboratory values.
- Change from baseline in ECG parameters and incidence of abnormal ECG findings.
- Change from baseline in vital signs.

### 3.3.2 Secondary Endpoints

Key secondary efficacy endpoints of the study are as follows:

PK:

- Pharmacokinetics – Peak plasma concentration of ifetroban after administration and its acyl glucuronide metabolite. Time of  $C_{max}$  ( $T_{max}$ ), AUC, Clearance, and Elimination half-life ( $t_{1/2}$ ). Dot blots of blood will be collected pre-dose and post-dose at 30, 60 ( $\pm 5$ ) minutes; 4, 8 and 24 hours (all  $\pm 30$  minutes) on Day 0 (first dose) and pre-dose and at 30 minutes ( $\pm 5$ ) post dose on Day 7 (steady state).

Efficacy:

- Efficacy of ifetroban over 12 months of dosing
  - ❖ Change from baseline in LVEF using cardiac MRI (CMR);
  - ❖ Change from baseline in myocardial strain using CMR;
  - ❖ Change from baseline in Pulmonary function test results including peak expiratory flow (PEF), forced vital capacity (FVC), forced expiratory volume in 1 second (FEV1), maximum inspiratory pressure (MIP), and maximum expiratory pressure (MEP);

- ❖ Change from baseline in Pediatric Quality of Life Inventory (PedsQL) results, including the gastrointestinal (GI) module and neuromuscular module (NMM).

### **3.3.3 Exploratory Endpoints**

Exploratory endpoints of the study are as follows:

Exploratory Biomarkers:

- Novel biomarkers for diagnosis and monitoring of cardiomyopathy in DMD including but not limited to change from baseline in miRNAs, eicosanoids, claudin-5, CD49d, CPK, hs-Trop, NT-proBNP and structural cardiac magnetic resonance (CMR) results.

Exploratory Efficacy:

- Change from baseline in daily life activity to evaluate motor function and estimate muscle strength measured by an actigraphy sensor worn for 1 week at baseline, Month 6 and Month 12.
- Change from baseline in Quantitative Muscle Testing (QMT) to assess muscle strength.

### **3.4 Sample Size**

The sample size is based on the comparison of each dose level of ifetroban (Low-Dose or High-Dose) to placebo with respect to change from baseline in LVEF using CMR for each disease stage, early (LVEF > 45%) or advanced (LVEF 35-45%).

Assuming observations from each treatment group have normal distributions with an effect size of 1.6 for the comparison of a dose of ifetroban to placebo, 8 subjects for each treatment group within disease stage will provide power exceeding 85% for a t-test at two-sided level 0.05. Under these assumptions, 8 subjects for each treatment group within disease stage will provide power exceeding 80% for the Wilcoxon rank sum test at two-sided level 0.05.

A total of 48 DMD subjects will be enrolled: 24 subjects with early stage DMD (LVEF > 45%) and 24 with advance stage DMD (LVEF 35-45%). Assuming a dropout rate of 10%, 54 subjects will be recruited to meet the target sample size of 48 subjects.

### **3.5 Randomization**

Subjects will be randomly assigned to one of three treatment groups: low-dose ifetroban 100 mg/day, high-dose ifetroban 300 mg/day or matching placebo, using a 1:1:1 randomization ratio. All subjects will be treated with IMP daily for a minimum of six months and a maximum of 12 months. Approximately 48 subjects shall be randomized to ensure at least 16 subjects per group will be analyzed for efficacy.

### **3.6 Analysis Sets**

### **3.6.1 Intention-To-Treat (ITT) Population**

The Intent-To-Treat (ITT) Population will consist of all treated subjects with at least one post-baseline assessment.

### **3.6.2 Per Protocol Population**

The Per Protocol (PP) Population will consist of all subjects in the ITT population with no major protocol violations, including violation of inclusion or exclusion criteria or insufficient dosing, where the latter includes missing more than 2 consecutive weeks of dosing for any reason or missing >20% of prescribed doses between visits.

### **3.6.3 Safety Population**

All subjects who receive at least one dose of treatment will be included in the Safety Population. The Safety population will be used in the statistical analyses for safety.

### **3.6.4 Pharmacokinetic Analysis (PK) Set**

The PK Analysis Set is the group of subjects who received at least 1 dose of test drug and had sufficient PK data to derive the plasma PK parameter.

## **3.7 Study Period Definition**

The following definitions for the study periods are as follows: Double-blind period for efficacy or safety endpoints is defined as the time from randomization or first dose date, respectively, to:

- the last dose of double-blind study drug if the subject continues to the OL period or,
- the last study visit if the subject does not continue to the OL period.

